7.15 Follow-up Phase Analysis

The follow-up phase analyses will be similar to those detailed above with a particular emphasis on the summarization of all adverse events occurring throughout the entire study and the maintenance of the treatment effect over time. Missing data analyses and imputation will not be performed on data collected during the extension phase.

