- A nasal speculum is inserted into the nostril and opened to visualize the treatment area. The Vivaer ARC Stylus will then be inserted to access the treatment area. The Stylus will be connected to the Aerin Console generator and the RF energy level will be set on the generator.
- Two (2) to six (6) nonoverlapping applications of RF energy are performed at the SSB per nostril.
- For the SSB, Vivaer ARC stylus default settings will be employed. ([Figure 4](#)).

Figure 4. Vivaer ARC Stylus applied at SSB

The default settings for the Vivaer ARC Stylus:

Temperature	60° C
Power	4 Watts
Treatment Time	18 secs
Cooling Time	12 secs

The Aerin Console is activated by depressing the foot pedal. With the Vivaer ARC Stylus pressed against the tissues in the desired treatment locations, the foot pedal is depressed, and the Stylus is gently pressed against the nasal tissues to deliver RF energy to the tissues consistent with the IFU. A tone sounds when the Console is activated, signifying that energy is being delivered through the Stylus. The tone stops when the pedal is released, and RF energy is no longer being delivered.

No repeat ("touch-up") procedures will be permitted during the study follow-up period. Additionally, for the purposes of this study, no other concomitant treatments are permitted during this treatment or the follow-up period.

Procedure data collection

Data relating to the procedure and the products used will be recorded on the Study Procedure eCRF. The following information will be recorded:

- Date of procedure.
- Procedure and postprocedure medications (including anesthesia).
- Aerin Console serial number.
- Procedure start and end times.
- Aerin Console settings.
- Treatment duration and number of sites treated for SSB.
- Occurrence of device malfunctions, protocol deviations, and/or adverse events.

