6.5 Postprocedure Assessments and Care

Immediately postprocedure, a nasal assessment (visual and endoscopic exam) for each nostril including endoscopic video will be conducted prior to discharging the participant and reported on the Study Procedure eCRF.

Participants will be asked to indicate the pain level experienced during the study procedure from anesthesia delivery to procedure completion using the VAS pain score instrument on the Pain VAS CRF.

At the discretion of the study physician, the following care may be provided and should be documented:

- Use of nasal saline spray and antibiotic ointment 2 to 3 times daily for 1 week.
- The participant should be instructed not to manipulate the treatment site (i.e., no nose blowing) for 24 hours with the exception of any necessary hemostasis.
- Remind participant to continue to hold all anticoagulants for 3 days post procedure.

Participants should have their first study follow-up visit (1 week +/- 3 days) scheduled within the visit window prior to release.

Participants should not receive other concomitant nasal treatment therapies (other than those specified above) or interventions after the procedure through the 36-month follow-up to avoid confounding the evaluation of the effect of the treatment, unless the additional care is in response to an adverse event or is considered in the best interest of the participant. Should a treatment or procedure be in the best interest of the participant, it must be documented in the source. The participant will remain in the study and be followed through 36 months. Concomitant nasal treatments will be monitored at follow-up evaluations.

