- Current use and participant-reported change in use of medication, and other therapies for symptoms of nasal obstruction and participant-reported changes in frequency of use.
- NOSE Scale score (verbal administration by site personnel).
- NRS ease of breathing score (verbal administration by site personnel).
- SNOT-22 (verbal administration by site personnel).
- Participant Satisfaction Survey (verbal administration by site personnel).
- Adverse events (study staff follow-up required if participant indicates an event).

Study exit:

Participants meeting the study requirements as planned will be exited from the study upon completion of the 36-month follow-up evaluation. If a participant reaches the 36-month follow-up evaluation and is experiencing a new or ongoing adverse event, the study sponsor should be contacted to discuss the need and/or methods for continued surveillance of the event.

Study exit applies to those participants where data is no longer collected for a study participant. A Study Exit form should be completed and entered into the electronic data capture (EDC) Systems in the following cases:

- Completion of 36 month participant questionnaires
- Signed consent but no procedure took place (eg, screen failure)
- Participant was unable to complete the follow-up visits
- Withdrawal of informed consent
- Physician exited participant based on medical or surgical necessity or other reason
- Participant received treatment outside of the study that, in the opinion of the investigator, would affect the study results.
- Lost to follow-up (3 attempts should be made and documented in the participant's record indicating due diligence by the site)
 - If a participant misses a questionnaire window and cannot be contacted, the participant may remain in the study, as contact may be re-established for a future questionnaire window period. (Any missed study assessment is considered a protocol deviation.) Participant withdrawal should be reported within 5 days of site becoming aware. participant death should be reported within 24 hours to Aerin Medical.
- Participant Death

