7.5 Analysis Populations

All enrolled participants entered in the study will comprise the safety population and will be subject to all safety analyses. All enrolled participants undergoing the procedure (initiation of anesthesia) represent the evaluable study population. For some evaluations, summaries will be presented by nostril. The per-protocol population is defined as all participants who received treatment, with 13-week (3-month) follow-up data and no major protocol deviations.

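### Durability results from 6 to 36 months will be observed-case only, and no rule covers NOSE scores recorded after outside treatment, where 6.5 and 6.6 can give opposite instructions

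*Combined protocol and SAP*

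**What the plan says.** **Missing data.** Section 4.2 makes durability over 36 months the secondary objective. The Protocol Summary adds a hypothesis that the effect is maintained, with no test or threshold. Section 7.15 says the follow-up analyses will stress maintenance of the effect, then closes: "Missing data analyses and imputation will not be performed on data collected during the extension phase". Section 7.6 tests the 13-week endpoints on available data and adds a check that scores a missing NOSE value as unchanged from baseline and the participant as a nonresponder. It ends by limiting other outcome measures to available data. NOSE change and responder proportions at 6, 12, 24 and 36 months are other outcome measures (Protocol Summary, 7.12).

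**Outside treatment.** Section 6.4 says "no other concomitant treatments are permitted during this treatment or the follow-up period". Section 6.5 makes exceptions for care given for an adverse event or in the participant's best interest. It requires best-interest treatment to be documented in the source and continues: "The participant will remain in the study and be followed through 36 months". It adds: "Concomitant nasal treatments will be monitored at follow-up evaluations". Section 6.6 asks that everyone be followed to 156 weeks whatever their earlier classification, yet its list of study exits includes this case: "Participant received treatment outside of the study that, in the opinion of the investigator, would affect the study results". It defines exit thus: "Study exit applies to those participants where data is no longer collected for a study participant". A missed contact is handled separately: "If a participant misses a questionnaire window and cannot be contacted, the participant may remain in the study".

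**Other provisions.** Section 7.5 states: "The per-protocol population is defined as all participants who received treatment, with 13-week (3-month) follow-up data and no major protocol deviations". What makes a deviation major is not defined. Section 7.12 makes a repeated-measures mixed model optional.

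**The concern.** The missing-data check applies at one in-office visit at 3 months. It does not apply at the four remote visits over the following 33 months, where loss has longer to build up and which alone address the secondary objective.

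The protocol itself foresees outcome-related loss. Section 5.8.1 warns that relief may not outlast the 3-month evaluation in every participant, and 10.6 anticipates withdrawal for lack of effect. A participant whose effect has faded may leave, or may be treated elsewhere. If treated elsewhere, a site following 6.5 would keep scoring a NOSE value that partly reflects the other treatment. A site following 6.6 would stop collecting data. Similar participants could then enter the 36-month summary as contaminated scores at one site and as missing at another, and no analysis rule brings the two together.

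At stake is how far a reader can trust a statement that the effect lasted three years.

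**Working it through.** **The plan's own figures.** The documents state no durability figure, dropout rate or outside-treatment rate. The planning figures in 7.3 concern 13 weeks only, and they reproduce at n = 70 with one-sided alpha 0.025:
- Primary endpoint (mean change -50 against -25, SD 20): noncentrality 25/(20/√70) = 10.46, power above 0.999 (stated 0.99).
- Secondary endpoint (80% against 55%): exact binomial rule of at least 48/70, power 0.992 (stated 0.99).

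Neither figure is in question here.

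**If participants exit (6.6 reading).** Let p be the true responder rate, and a and f the shares of responders and nonresponders who exit.
- Observed rate = p(1-a) / [p(1-a) + (1-p)(1-f)].
- Rate with missing scored as nonresponse = p(1-a).

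n = 70 is from 7.3. A true 80% is the plan's 13-week expectation; a true 60% and all exit shares are assumptions. Counts are expected values.

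| Exit: responders / nonresponders | True 60%: observed | Missing = nonresponse | True 80%: observed | Missing = nonresponse |
|---|---|---|---|---|
| 0 / 25% | 42/63 = 67% | 60% | 56/66.5 = 84% | 80% |
| 0 / 50% | 42/56 = 75% | 60% | 56/63 = 89% | 80% |
| 10% / 25% | 37.8/58.8 = 64% | 54% | 50.4/60.9 = 83% | 72% |
| 10% / 50% | 37.8/51.8 = 73% | 54% | 50.4/57.4 = 88% | 72% |
| 30% / 10% | 29.4/54.6 = 54% | 42% | 39.2/51.8 = 76% | 56% |
| 20% / 20% | 33.6/56 = 60% | 48% | 44.8/56 = 80% | 64% |

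The observed rate can be too high, too low or right. The alternative never exceeds the true rate, and under random loss it falls well below it.

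**If participants stay (6.5 reading).** Let g be the share of nonresponders treated elsewhere and s the share of those who then meet the responder definition. Reported rate = p + (1-p)·g·s. At p = 60%, g = 25% or 50% gives 65% or 70% with s = 0.5, and 70% or 80% with s = 1.

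**What planned tables can recover.** Suppose 56 of 70 are seen, 45 of them responders (80.4%), with mean change -50. From the visit counts (7.8) and summaries (7.16) a reader can compute 45/70 = 64.3% and -50 × 56/70 = -40. Now suppose all 70 are seen, 49 respond (70%) and 14 were treated elsewhere. Between 0 and 14 of those 14 may be among the responders. The re-scored rate therefore lies anywhere from 35/70 = 50% to 49/70 = 70%. Even this supposes the count of 14 is reported, and the disposition summary in 7.8 does not plan it.

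**Whether no change is a lower limit for the mean.** It is not. If the 14 missing participants worsened by 10 points, the mean would be (56 × -50 + 14 × 10)/70 = -38, worse than -40.

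**Where 6.5 and 6.6 collide.** Section 6.5 covers care for an adverse event or in the participant's best interest. Section 6.6 turns on the investigator's opinion that the treatment would affect results. Treatment meeting only one condition raises no conflict. Treatment meeting both, such as a best-interest nasal procedure that alters symptoms, carries two incompatible instructions: follow to 36 months, or exit and stop collecting data.

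**The case against.** The strongest reply is that 7.12 calls these outcomes informational and hypothesis-generating, no durability test exists, and a reader can already rebuild the missing-as-nonresponse figure from planned tables. The follow-up provisions also work against the feared mechanism. Section 6.6 follows everyone regardless of earlier success or failure and requires three documented contact attempts. Section 10.6 asks that participants withdrawing for lack of effect still be followed, and 10.5 allows payment for completed questionnaires. Every rate in the illustration is assumed.

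Much of this stands. It limits the weight of the point, and it makes the missing-data part partly a matter of presentation. It does not supply a rule for scores after outside treatment, and those cannot be re-scored from planned tables. The per-protocol set does not help, because it is defined on 13-week data. The mixed model is optional and does not address such scores. Follow-up efforts reduce outcome-related loss but do not remove it, and they cannot prevent loss that 6.6 itself prescribes.

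A reader might infer that 7.15 alone causes the observed-case analysis, or that 6.4, 6.5 and 6.6 conflict throughout. The documents do not support either inference. Section 7.6 independently limits other outcomes to available data. Sections 6.5 and 6.6 collide only where both conditions apply. Section 6.4 is a permission rule, silent on data collection; its difficulty is that it omits the exceptions in 6.5.

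**Conclusion.** The point holds as a worthwhile improvement. Sections 7.6 and 7.15 together leave the secondary objective on observed cases. Sections 6.5 and 6.6 give incompatible instructions in an identifiable case, and no section says how NOSE scores recorded after such treatment are analyzed.

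A reader might infer that the 36-month results will be overstated. The documents do not support that. They give no exit or outside-treatment rates, and at an assumed true 60% the exit scenarios above run from 54% to 75%, with no bias when exit is unrelated to outcome. The size depends wholly on those assumed rates. The 13-week endpoints keep their own missing-data check and are unaffected.

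**What to change.** 1. Reconcile 6.5 with 6.6 on whether data collection continues after outside treatment, and align 6.4 with the exceptions in 6.5. Which clinical rule is right is for the sponsor and investigators.
2. Replace the last sentence of 7.15 and amend the closing sentence of 7.6; changing only one would leave the two in contradiction. At 6, 12, 24 and 36 months, show observed-case NOSE change and responder results beside a sensitivity analysis on all treated participants that applies the 13-week rule (missing = no change and nonresponder). Label it a lower bound for the responder proportion. For the mean change, label it a conservative sensitivity analysis and not a bound, because scores can worsen.
3. In that analysis, handle NOSE scores recorded after qualifying outside treatment in the same way. Define the qualifying treatments in advance, for example nasal procedures, with a stated rule for newly started medications. Impute a participant who misses a window and later returns only at the missed visit.
4. Record outside nasal procedures on the existing follow-up eCRF, since 6.5 requires best-interest treatment to be documented only in the source. Add the number of participants with outside treatment, by visit, to the 7.8 disposition summary.

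The mixed model can stay optional. The cost is wording in 6.4 to 6.6, 7.6 and 7.15, one definition, an eCRF entry and a few tables. The drawback is that the sensitivity result understates durability when loss is random: 20% random loss shows 48% at a true 60% (0.60 × 0.80). If 10% of lasting responders have a qualifying treatment, a true 60% shows as 54% (0.60 × 0.90). The observed-case results should therefore remain beside it.

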7.16 Standard Methods of Report

Summary descriptive statistics including means, medians, standard deviations and histograms for continuous measures, and frequencies and percentages for categorical outcomes will be presented for all variables of interest. Outcome measures (primary, secondary, and informational) will be presented by evaluation.

8.0 Adverse Events and Product Complaints / Device Deficiencies

8.1 Adverse Events

All adverse events, collected from the time of study consent (study entry) until the end of the study will be analyzed for all participants. Adverse events may occur during the treatment phase or during the follow-up phase. AEs occurring after the screening assessment but before the preprocedure (application of anesthesia) will be documented in the participant's medical record and EDC but will not count as related to the study device or procedure.

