Vivaer Treatment:	The Vivaer procedure will be performed in the study clinic using the Vivaer ARC Stylus and Aerin Console. The Vivaer ARC Stylus is a disposable handheld device capable of delivering bipolar radiofrequency energy to tissue when connected to the Aerin Console radiofrequency generating device. Participants will undergo bilateral treatment of the nasal airway in a single study procedure session. Each side of the nose will be treated as follows:

Clinical Study Protocol – SWELL Study

- Two (2) to six (6) nonoverlapping applications of RF energy are performed at the SSB per nostril.

The default treatment settings will be used for the study: temperature 60° C, power 4 watts, treatment time 18 seconds, and cooling time 12 seconds. No repeat (“touch up”) procedures will be permitted after the initial procedure through the end of the study (36 months).

Primary Endpoint:	The primary endpoint is improvement in self-reported Nasal Obstruction Symptom Evaluation (NOSE) Scale score from baseline recorded at the screening evaluation to 13 weeks after the procedure.
Secondary Endpoints:	
• Responder percent: A responder is defined as at least 1 NOSE Scale class improvement or an improvement (decrease) in NOSE Scale score of 20% or more from baseline to 13 weeks after the procedure.• Frequency of device-related and procedure-related serious adverse events, including frequency of septal perforation during the procedure, through the 3-month evaluation.
Study Hypotheses	Primary hypothesis: mean improvement in NOSE Scale score from screening to 13 weeks will exceed 25 points. Other hypothesis: the treatment effects will be maintained through the extended follow-up period of 36 months.

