5.2.1 Inclusion Criteria

1. Age 22 to 85 years (inclusively).
2. Seeking treatment for nasal obstruction and willing to undergo an office-based procedure.
3. Baseline NOSE score ≥ 55 .
4. Presence of SSB hypertrophy limiting visualization of the middle turbinate (MT) by more than 50%.
5. Reduction in size of the SSB after application of topical decongestant on a cotton plug directly to the SSB region.
6. Improvement in the symptoms of nasal obstruction after SSB decongestion suggesting that the SSB may play a role in nasal obstruction.
7. Willing and able to withhold anticoagulant medications during the perioperative period (3-day window on either side).
8. Willing and able to provide informed consent.
9. Willing and able to comply with the participant-specific requirements outlined in the study protocol.

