7.14 Safety Analysis

All adverse events, collected from the time of study consent (study entry) until the end of the study will be analyzed for all participants. Adverse events may occur during the treatment phase or during the follow-up phase. AEs occurring after the screening assessment but before the procedure (application of anesthesia) will be

Clinical Study Protocol – SWELL Study

documented in the participant's medical record and EDC but will not count as related to the study device or procedure. Adverse events will be coded using a custom Aerin Medical dictionary so that adverse events may be categorized for analysis at an appropriate level of detail. Listings will be provided to detail individual events. The number of participants, number of AEs, and the proportion of participants reporting each AE will be summarized. Seriousness and severity of AEs and their relationship to the device and procedure will be summarized. A time course of adverse events will be presented. Any unexpected adverse device experiences or adverse events that occur at an unexpectedly high incidence rate will receive detailed analyses. Narratives will be presented for all deaths, serious adverse events, unexpected adverse device experiences, and participants withdrawn due to an adverse event.

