8.1.1 Definitions

Following are definitions associated with AEs:

Adverse Event - any untoward medical occurrence, unintended disease or injury, or untoward clinical signs (including abnormal laboratory or image findings) in participants, users or other persons, whether or not related to the investigational medical device and whether anticipated or unanticipated (per ISO 14155)

Note: This definition includes events related to the investigational medical device or the comparator. This definition also includes events related to the procedures involved. For users or other persons, this definition is restricted to events related to the use of investigational medical devices.

Clinical Study Protocol – SWELL Study

Serious Adverse Event (SAE) - an adverse event that led to any of the following (per ISO 14155)

- a) death,
- b) serious deterioration in the health of the participant, users or other persons as defined by one or more of the following:
 - 1) a life-threatening illness or injury, or
 - 2) a permanent impairment of a body structure or a body function including chronic disease, or
 - 3) in-patient or prolonged hospitalization, or
 - 4) medical or surgical intervention to prevent life-threatening illness or injury or permanent impairment to a body structure or a body function,
- c) fetal distress, fetal death, or a congenital abnormality, or birth defect including physical or mental impairment.

Note: Planned hospitalization for a pre-existing condition, or a procedure required by the protocol, without serious deterioration in health, is not considered a serious adverse event.

Adverse Device Effect (ADE) – adverse event related to the use of an investigational medical device.

Note: This definition includes adverse events resulting from insufficient or inadequate instructions for use, deployment, implantation, installation, or operation, or any malfunction of the investigational medical device. This definition also includes any event resulting from use error or from intentional misuse of the investigational medical device. This includes comparator if the comparator is a medical device

Serious Adverse Device Effect (SADE) – an adverse device effect that has resulted in any of the consequences characteristic of a serious adverse event (per ISO 14155).

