Unanticipated Adverse Device Effect (UADE) - any serious adverse effect on health or safety or any life-threatening problem or death caused by, or associated with, a device, if that effect, problem, or death was not previously identified in nature, severity, or degree of incidence in the investigational plan or application (including a supplementary plan or application), or any other unanticipated serious problem associated with a device that relates to the rights, safety, or welfare of participants (21 CFR 812.3(s)).

Relationship to device and procedure

The potential relationship of the event to the device or procedure will be categorized by the investigator as follows:

Clinical Study Protocol – SWELL Study

- Not related

An adverse event for which sufficient information exists to indicate that there is no causal connection between the event and the device or procedure. The adverse event is due to and readily explained by the participant's underlying disease state or is due to concomitant medication or therapy not related to the use of the device or the procedure. In addition, the adverse event may not follow a reasonable temporal sequence following the procedure.

- Unlikely

The relationship with the use of the device or procedure seems not relevant and/or the adverse event can be reasonably explained by another cause, but additional information may be obtained.

- Possibly related

There is a reasonable possibility that the adverse event may have been primarily caused by the device or procedure. The adverse event has a reasonable temporal relationship to the use of the device or the procedure and follows a known or expected response pattern to the device or procedure, but alternative etiology is equally or more likely compared to the potential relationship to the use of the device or the procedure.

- Probably related

There is a reasonable probability that the adverse event may have been primarily caused by the device or procedure. The adverse event has a reasonable temporal relationship to the use of the device or the procedure and follows a known or expected response pattern to the device or procedure, and an alternative etiology is unlikely or significantly less likely.

- Definitely related

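### A serious adverse event from the pre-procedure anticoagulant hold that starts before anesthesia is kept out of the procedure-related SAE endpoint by timing alone

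*Combined protocol and SAP*

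**What the plan says.** Section 7.14 opens the rule with "AEs occurring after the screening assessment but before the procedure (application of anesthesia) will be", and the sentence ends as in 8.1: such events are "documented in the participant's medical record and EDC but will not count as related to the study device or procedure". Section 8.1 sets the end of the period slightly differently, at "AEs occurring after the screening assessment but before the preprocedure (application of anesthesia"), but both sections anchor it at anesthesia. Neither makes an exception.

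Inclusion criterion 7 in 5.2.1 reads "Willing and able to withhold anticoagulant medications during the perioperative period (3-day window on either side"). Section 6.5 adds, for aftercare, "Remind participant to continue to hold all anticoagulants for 3 days post procedure".

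The Protocol Summary lists as a secondary endpoint "Frequency of device-related and procedure-related serious adverse events, including frequency of septal perforation during the procedure, through the 3-month evaluation". Section 7.11 reports this as a proportion with a 95% confidence interval.

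For causality, 8.1.1 states: "The potential relationship of the event to the device or procedure will be categorized by the investigator as follows". Five levels follow, and an event that the investigator cannot place is treated as possibly related.

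**The concern.** The timing rule decides relatedness before anyone looks at the event. For the device this is sound, since a device that has not been used cannot have caused anything. For the procedure it is less clear, because the protocol places a preparatory step, the anticoagulant hold, inside the period that the rule covers. A serious event arising from that step would be reported as unrelated, while the same harm a day or two later would go to the investigator.

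At stake is the accuracy of a named safety endpoint. The misclassification has one direction: the rule can remove a related event from the count but cannot add one.

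**Working it through.** The plan gives no figure on this point, so the check is mainly a comparison of texts.

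**1. Does the hold fall inside the rule's period?** The rule runs from after the screening assessment to anesthesia. Treatment may follow screening by up to 30 days (6.4). Criterion 7 places 3 days of withholding before the procedure. Section 6.5 speaks of continuing the hold, which presupposes that it has begun. Section 6.4 gives no separate instruction to start it, so the pre-procedure hold rests on the eligibility criterion and that one word.

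**2. How is harm from the hold classified, by onset?**

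| Onset | What the plan does | Can it enter the procedure-related SAE endpoint? |
|---|---|---|
| During the screening assessment | Not expressly covered by the timing rule | Not excluded by that rule |
| After screening, before anesthesia; participant later anesthetized | In the safety population; labelled unrelated by timing | No |
| After screening, before anesthesia; participant never anesthetized | Not enrolled (5.3), so outside the safety population (7.5) | No, whatever the relatedness rule says |
| After anesthesia, including the 3 further hold days | Investigator categorizes; possibly related if unassignable | Yes |

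If screening and treatment fall on the same day, as 6.4 allows, the earlier hold days precede consent and event collection. The rule then has no bearing on them.

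**3. How does the rule sit with 8.1.1?** There, the lowest category needs enough information to show that no causal link exists, and doubt defaults to possibly related. The timing rule assigns the unrelated outcome with no information about the event.

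**4. How much of the hold is affected?** With 3 days before and 3 after, 3/(3 + 3) = 50% of hold days precede anesthesia. Counting day 0 as a post-anesthesia day gives 3/(3 + 1 + 3) = 43%. These are shares of days, not of risk.

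**5. Illustration of one event.** Assume 70 treated participants (the planned maximum in 7.3) and one affected participant who is later anesthetized and so stays in the denominator. Exact (Clopper-Pearson) 95% intervals:

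- 0/70 = 0%; upper limit 1 − 0.025^(1/70) = 5.1%.
- 1/70 = 1.4%; lower limit 1 − 0.975^(1/70) = 0.04%; upper limit, the 0.975 quantile of Beta(2, 69), = 7.7%.

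One reclassified event moves the estimate by 1.4 percentage points. The number of participants on anticoagulants and the event rate during a hold are not given, so no expected count can be calculated. If nobody is on anticoagulants, this route has no effect.

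**The case against.** The best defense is that counting related events from the start of the intervention is a recognizable convention, and that 7.14 and 8.1 are a specific exception to the general scheme in 8.1.1. The endpoint carries no hypothesis or threshold, and study success (5.5.2) rests on the NOSE change alone. The categories in 8.1.1 also refer to timing relative to the procedure, so an earlier event fits them poorly even without the rule. All of this is fair. It limits the consequence, and it shows that deleting the timing rule would not be enough. It does not explain why a harm of protocol-driven preparation should be graded on one side of anesthesia and not on the other.

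A reader might infer more than the documents support:

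- *Harm from the hold can never count.* It can if it starts after anesthesia.
- *Every event before anesthesia is excluded.* The rule begins only after the screening assessment.
- *The rule contradicts the adverse event definition.* The note "This definition also includes events related to the procedures involved" settles what is an adverse event, not what is related. The tension is with the causality assessment alone.
- *The events disappear.* Events are collected from consent, all SAEs go to the sponsor within 24 hours (8.1.2), and all SAEs receive narratives (7.14), whatever their relatedness.
- *A result of 1/70 would be reported as 0/70.* That holds only for someone who has the event and is still treated. A participant with a serious event just before the procedure may never be anesthetized.

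**Conclusion.** The point stands in a narrow form. A serious event from the pre-procedure hold, with onset after the screening assessment and before anesthesia, is excluded from the procedure-related SAE endpoint by timing alone and without the causality assessment that 8.1.1 prescribes. Only the event's classification and the endpoint proportion are affected, not its detection or reporting.

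The size is unknown and probably very small. The conclusion assumes that some participants are on anticoagulants, that screening precedes treatment by long enough for the hold to fall after the screening assessment, and that criterion 7 with 6.5 describes a hold actually carried out. It is worth correcting because the error runs only toward no harm and the change is cheap.

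**What to change.** - **7.14 and 8.1:** keep events before anesthesia as not device-related, but have the investigator categorize their relationship to the procedure, including protocol-required preparation. Use the same wording for the end of the period in both sections.
- **8.1.1:** state that the temporal language in the categories does not rule out events during that preparation.
- **Reporting:** show pre-anesthesia events judged at least possibly related on a separate line, with all consented participants as the denominator. Include serious ones in the procedure-related SAE endpoint when the participant is later anesthetized.
- **5.3 and 7.5 against 7.14 and 8.1:** reconcile a safety population that begins at anesthesia with the commitment to analyze events from consent for all participants, so that someone harmed and never treated has a defined place.

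The cost is a few sentences across these sections and one more line in the adverse event table. The downside is that the procedure-related count could be slightly less favorable. No change to the hold itself is proposed.
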